PILOT STUDY OF CYANOACRYLATE OCCLUSION OF THE LOWER LIMB VEINS IN PATIENTS WITH VENOUS ULCERS- FINAL PROTOCOL

[name], [name], [name]

21st June 2017

BACKGROUND / RATIONALE

Minimally invasive techniques are now routine for the treatment of lower limb varicose veins. Endovenous laser therapy and radiofrequency ablation enable lower limb venous occlusion to be performed under local anaesthesia, minimising operative risk and reducing healthcare costs. However, both techniques generate heat which may injure adjacent nerves, risking long term disability. Non-thermal venous occlusion technology avoids the need for tumescent local anaesthesia and further reduces both risk and healthcare costs.

The Medtronic VenaSeal[™] system uses an n-2-butyl-cyanoacrylate adhesive to occlude incompetent veins. It does not require local anaesthetic tumescence and there is very low risk of peripheral nerve injury. The delivery catheter is introduced into the target vein under ultrasound guidance, and slowly withdrawn as the adhesive is injected. Manual compression is applied to each treated segment of vein for 30 seconds to ensure adhesion.

The current literature suggests that cyanoacrylate embolization is a safe, effective treatment for lower limb venous incompetence. One randomized control trial in patients with varicose veins has been completed and demonstrated that cyanoacrylate embolization was as effective as radiofrequency ablation in maintaining great saphenous vein occlusion 3 months post-procedure.¹ Non-comparative studies with longer follow-up periods have shown recanalization rates of less than 8% during the first year after treatment.^{2,3} In addition, Venous Clinical Severity and Aberdeen Varicose Vein Questionnaire scores were significantly improved following cyanoacrylate treatment and were similar to scores in patients treated by radiofrequency ablation.¹ Patients in the other clinical studies also showed an improvement in symptom scores.^{2,3} Importantly, adverse effects were minimal, with mild phlebitis reported in 6-16% of patients.¹⁻³ No patients in any study developed deep vein thrombosis or pulmonary embolism ¹⁻³ and only 1/222 patients in the randomised trial developed an injection site infection, successfully treated with oral antibiotics.¹

There has been no research on the value of cyanoacrylate embolization in the treatment of patients with chronic venous insufficiency and ulceration. Venous leg ulceration costs the NHS £600 million per year and affect 1.7% of the elderly population^{4,5}, making it a significant health problem that justifies further study.

We propose to define whether cyanoacrylate embolization is a safe and effective method of occluding incompetent lower limb veins in patients with venous ulceration of the lower limb.

PRIMARY OBJECTIVES

Our primary objectives are to answer the following research questions:

1. Does VenaSeal[™] cyanoacrylate occlusion of incompetent lower limb veins increase the rate of healing and shorten healing time in patients with an ipsilateral venous ulcer?

2. What is the incidence of venous recanalization following VenaSeal[™] cyanoacrylate occlusion for the treatment of ipsilateral venous leg ulcer?

3. Does VenaSeal[™] cyanoacrylate occlusion of incompetent lower limb veins improve quality of life and symptom severity scores in patients with venous leg ulcer?

4. What is the adverse effect profile of VenaSeal[™] cyanoacrylate occlusion of incompetent lower limb veins for the treatment of venous leg ulcers?

The overall aim of the research is to determine whether VenaSealTM cyanoacrylate occlusion of incompetent lower limb veins is an effective, safe and acceptable treatment in patients with ipsilateral venous leg ulcer.

STUDY DESIGN

This study is a randomised controlled trial comparing VenaSeal[™] cyanoacrylate occlusion plus normal treatment with normal treatment alone in patients with ipsilateral venous leg ulceration and Duplex-detected lower limb vein incompetence.

Normal treatment in both groups is defined as nurse-led dressing of the ulcer using a low adherence dressing and four-layer compression bandaging. Patients randomized to the treatment arm will also undergo cyanoacrylate occlusion using the VenaSealTM system.

The study will begin with 5 patients undergoing VenaSeal treatment as 'roll in' cases. Following these patients' treatment, the study proper will begin. Randomisation software will be used to allocate patients who fulfil inclusion / exclusion criteria to either the treatment arm or the non-treatment arm. This will be done to a 1:1 ratio, with 25 patients in each arm.

Patients will be followed up via face-to-face consultations at 3, 6 and 12 months post-randomisation.

INCLUSION CRITERIA

- 1. Venous ulcer of the lower limb at least 2cm² (CEAP classification C6)
- 2. Ulceration present for >6 weeks and <6months despite treatment.
- 3. Ipsilateral lower limb vein incompetence of >0.5 seconds duration, confirmed by venous duplex imaging.
- 4. Aged ≥18 years.
- 5. Willing and able to provide informed consent.
- 6. Ipsilateral ankle-brachial pressure index ≥ 0.8 at the time of randomisation.

EXCLUSION CRITERIA

- Non-venous cause of ulceration: peripheral arterial disease (ABPI < 0.8), vasculitis, neuropathy, recent lower limb trauma, chronic dermatitis, pyoderma gangrenosum, malignancy, chronic osteomyelitis or any other lower limb pathology that may be contributing to the ulceration, in the opinion of the investigator.
- 2. Inability to tolerate or comply with lower limb compression therapy
- 3. Inability to receive prompt endovenous treatment
- 4. Unwilling or unable to provide informed consent.
- 5. Current enrolment in another study pertaining to venous ulceration.
- 6. Primary or secondary immunosuppression.
- 7. Previous treatment of the target vein or other venous surgery that may compromise the study, in the opinion of the research team.
- 8. Patient has pre-planned surgical intervention or endovascular procedure scheduled up to 30 days after the index procedure.
- 9. Currently pregnant.
- 10. Duplex evidence of deep venous incompetence or occlusion.
- 11. Clinical evidence of post-thrombotic syndrome.
- 12. Incompetent vein considered too tortuous to allow VenaSealTM treatment.
- 13. Inability to tolerate VenaSeal[™] treatment.

PRIMARY ENDPOINTS

The primary outcome measure is the rate of healing in leg ulcer surface area. The margins of the ulcer will be traced onto an acetate sheet and measured using a planimeter¹. From these weekly measurements (every 7 days +/- 2 days), it will be possible to calculate the

¹ The ulcer margins are traced onto a sheet of acetate. The acetate is then placed on a flat surface, and a planimeter is used to measure the surface area within the outlined margins. The planimeter is calibrated prior to use to ensure accuracy. For this study, a Planix 7 (Tamaya Technics, Tokyo, Japan) will be used.

rate at which the ulcer is healing. The time to healing (defined as complete overgrowth of the epithelial surface in the opinion of the researcher) will also be recorded. All measurements will be taken in duplicate by two members of the research team. The point at which the ulcer has healed represents the patient reaching the primary endpoint. Once healing has occurred, the patient will not be required to return to the clinic for weekly assessments, but will be asked to complete the questionnaires that measure the secondary endpoints at 3, 6 and 12 months (as described below), until the one year follow up period is complete.

Measuring rate of healing is important as it allows legitimate comparison between patients with differently sized ulcers. Time to healing is extremely important, as healing reduces the burden of symptoms and the impact on quality of life, and is the primary target for all patients and clinicians managing venous leg ulcer. Ulcer recurrence will not be assessed, as the follow up period is limited to 12 months.

PATIENT SAFETY

All patients will be treated in line with local and National Health Service (NHS) health and safety policies. All VenaSealTM treatments will adhere to the Instructions For Use (IFU) supplied with the product. All patients will have immediate access to acute medical and surgical services provided by the University Hospital of South Manchester NHS Foundation Trust in the event of adverse effects or complications of treatment.

PROCEDURE / INTERVENTION DESCRIPTION

All patients will be randomised to receive standard venous leg ulcer management, or standard venous leg ulcer management plus VenaSeal occlusion of incompetent lower limb veins.

Patients randomised to the treatment arm will undergo cyanoacrylate treatment using the VenaSealTM closure system (Medtronic, Dublin, Ireland), according to the Instructions for Use (IFU). The patient will lie supine on an examination couch, wearing a standard hospital gown. The skin will then be prepared using chlorhexidine gluconate 4% solution and a sterile field created with adhesive drapes. The operator will then use a portable ultrasound system to identify a target and will mark it using a sterile marker pen. The course of the target vein will also be assessed using the ultrasound probe. The skin over the target site will be infiltrated with 1% lidocaine with 1:200,000 adrenaline solution (maximum dose 7mg/kg) until sufficiently anaesthetised in the opinion of the operator and the patient.

Choosing the appropriate access site will depend on patient factors. Care must be taken to not enter the vein through an area of compromised skin, ulceration, and/or area of

infection. An access point near or at the ankle may be chosen, taking care not to choose a site immediately overlying bone. Regardless of access point, the goal is to treat as much of, if not the entire segment of pathologic vein. If the operator considers it possible to give additional injections over incompetent calf perforators with cyanoacrylate during the saphenous treatment, then that will be attempted. If low cannulation of the vein is not considered possible due to proximity with the ulcer, then this will not be attempted.

An additional aim of this study is to determine whether VenaSeal can be used as an officebased treatment without the requirement for adjunctive, theatre-based interventions. As such, foam sclerotherapy, phlebectomies and other adjuncts will not be used.

The operator will use Seldinger technique to gain access and position the VenaSeal[™] delivery catheter into the target vein at the marked site. The catheter will be passed along the length of the target vessel that is required to be treated. The operator will confirm its position with the ultrasound probe. For GSV/AAGSV treatment, position the catheter 5 cm caudal from the saphenofemoral junction (saphenopopliteal junction for SSV treatment), and perform treatment according to the IFU.

Once the desired length of vein has been treated, the device will be withdrawn and the wound compressed manually until haemostasis has been achieved. A small dressing will be placed at the puncture site, followed by dressing of the venous ulcer with a low adherence dressing and four-layer compression bandaging applied by a specialist leg ulcer clinic nurse, aiming for a pressure of 40mmHg at the ankle and graduated towards the knee. Written advice will be provided to emphasise the need for patients to elevate their lower limb whenever possible, along with additional advice on how to manage the compression bandages. Patients will return to the leg ulcer clinic weekly to continue the usual leg ulcer treatment of wound care, dressings and compression bandaging.

Patients randomised to the non-treatment arm will receive the usual treatment for venous leg ulcer, specifically routine wound care, dressings, and the application of four-layer compression bandaging applied by a specialist leg ulcer clinic nurse, aiming for a pressure of 40mmHg at the ankle. The same written advice will be provided to this group. All compression bandages for patients in both arms will be applied by nursing staff who work in the specialist leg ulcer service.

If any participant requires further vascular surgical intervention, including treatment of perforators (e.g. treatment with ClosureFast[™] RFS Stylet), then this will be arranged and offered as for any other non-research participant. The requirement for further interventions directly related to the patient's venous disease will be recorded by the research team, if it occurs within the 12 month follow up period.

SECONDARY ENDPOINTS

The secondary measures will be measured at baseline, 3, 6 and 12 months and are as follows:

1. The validated EQ-5D, SF-36 and VEINES-QoL scores^{6,7} will be used to assess quality of life, self-assessment of health, and severity of symptoms in both groups. Venous leg ulcer is associated with reduced quality of life and prolonged, often severe symptoms, so this is an important assessment.

2. The rate of venous recanalization seen on duplex ultrasound is also important, to ensure that the venous occlusion has persisted.

3. Patient satisfaction scores

4. Adverse event recording will also take place, which is an important step in defining the safety of the procedure for this purpose. These will be described in the final report and in any other presentations of the work.

5. Health economic analysis:

- a) Cost and frequency of visits to wound care and outpatient clinic.
- b) District nurse visit costs
- c) Inpatient treatment costs

d) Costs of complications of the treatment, or of non-healing ulcers (for example, acute or chronic infections).

STATISTICAL METHOD / RATIONALE

The main aim of the pilot study is to inform a larger, more definitive study by assessing feasibility and describing the main outcomes for the patients in the study. As such, the main analysis will be summary statistics. Simple statistical tests will be used to compare the groups, though these analyses are exploratory and non-definitive since the study is a pilot and has a limited sample size.

Time from intervention to healing, one part of the primary outcome, will be described in the two randomised groups using medians, interquartile ranges and ranges (minimum to maximum), assuming the data will be non-normally distributed. The other component of the primary outcome, the mean % ulcer healed per week², will be calculated for each patient

² The mean % ulcer healed per week will be calculated up to the point where the ulcer has fully healed (the primary endpoint). No further measurements will be calculated after this point.

and summarised in the two groups using means, standard deviations and ranges, assuming the data will be normally distributed.

The secondary endpoints will also be assessed using descriptive statistics. The composite VEINES-QOL/Sym score will be calculated using the intrinsic scoring method detailed in the Bland et al. validation paper.⁷ The composite summary scores will be described at each point they are assessed using means, standard deviations and ranges.

The rate of venous recanalization in each group will be summarised using frequencies and percentages. The number of adverse events and percentage in each group will be presented.

The statistical analyses used to compare the groups will be independent samples t-tests, Mann-Whitney U tests, and chi-squared tests.

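### Exclusion 8 screens out already-booked procedures for only 30 days of a 12-month comparison, so a patient already listed for treatment of the study vein can enter the control arm

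*Protocol*

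**What the plan says.** The Study Design section of the protocol describes a trial "comparing VenaSeal[™] cyanoacrylate occlusion plus normal treatment with normal treatment alone". On allocation it states: "Randomisation software will be used to allocate patients who fulfil inclusion / exclusion criteria to either the treatment arm or the non-treatment arm". On size: "This will be done to a 1:1 ratio, with 25 patients in each arm". On follow-up: "Patients will be followed up via face-to-face consultations at 3, 6 and 12 months post-randomisation".

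The control treatment is set out under Procedure / Intervention Description: "Patients randomised to the non-treatment arm will receive the usual treatment for venous leg ulcer, specifically routine wound care, dressings, and the application of four-layer" (the sentence goes on to the bandaging). It contains no vein procedure.

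Under Exclusion Criteria, item 8 is the only rule on procedures already arranged: "Patient has pre-planned surgical intervention or endovascular procedure scheduled up to 30 days after the index procedure". The index procedure is not defined. Item 7 concerns venous treatment in the past, and item 3 removes anyone who could not have endovenous treatment promptly.

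If a participant in either arm needs further vascular intervention during the study, "then this will be arranged and offered as for any other non-research participant". The same paragraph has the research team record further interventions for venous disease within the 12 months.

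**The concern.** The contrast of interest is vein occlusion plus compression against compression without it. Every participant has duplex-confirmed incompetence on the ulcerated side (inclusion 3) and must be able to receive prompt endovenous treatment (exclusion 3), so the trial selects people who are candidates for the very treatment that the control arm should not receive. If some already hold a date for it beyond the 30-day window, nothing in the criteria keeps them out.

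A control whose study vein is treated on a date fixed before randomisation still counts as a control for healing time, healing rate, quality of life and cost. For that patient the comparison becomes early against scheduled occlusion, and the arms look more alike than they should. The pilot is meant to inform a larger study, so its descriptive control-arm results are what get carried forward. Treatment booked before entry is also known at screening, which makes it the one part of this contamination that eligibility alone can prevent.

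**Working it through.** **1. Reading the criteria together.** Take a patient who at screening is listed for ablation of the study vein at week 6 (day 42).
- Exclusion 7: not triggered, because the treatment has not happened yet.
- Exclusion 8: not triggered, because 42 days is more than 30 (taking the expected index procedure to fall at about randomisation).
- No other criterion mentions planned procedures.

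The patient is eligible and has a one-in-two chance of allocation to control.

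**2. Anchor.** Follow-up is counted from randomisation and exclusion 8 from the index procedure. Eligibility is settled before allocation, so the rule can be applied to every candidate against an expected procedure date. The missing procedure in controls makes the wording unclear; it does not itself let anyone in. The 30-day length does.

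**3. Window against follow-up.** 30/365 = 8%, leaving 335/365 = 92% of follow-up uncovered. This share is not a measure of bias (see step 6).

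**4. Weight of one patient.** 1/25 = 4% of the control arm.

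**5. Effect on median healing time.** The protocol gives no healing, effect or booking figures, so there is nothing of its own to reproduce and everything in this step is an assumption: exponential healing; control median *m* of 12 or 24 weeks; hazard ratio HR of 1.5 or 2.0; a share *c* of controls treated at week 6 if still unhealed, who then heal at the treated rate.

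Control hazard: λ = ln 2 / *m*. Treated median: *m*/HR. For t > 6 the proportion of controls unhealed is

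S(t) = (1 − c)·exp(−λt) + c·exp(−6λ − HR·λ·(t − 6)),

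and the control median solves S(t) = 0.5.

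| | m = 12, HR = 1.5 | m = 24, HR = 2.0 |
|---|---|---|
| λ per week | 0.0578 | 0.0289 |
| Treated median, weeks | 12/1.5 = 8.0 | 24/2.0 = 12.0 |
| Difference, c = 0 | 12.0 − 8.0 = 4.0 | 24.0 − 12.0 = 12.0 |
| Control median, c = 4% | 11.89 | 23.45 |
| Difference, c = 4% | 3.89 | 11.45 |
| Loss | 0.11/4.0 = 3% | 0.55/12.0 = 5% |

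Check of the first column: 0.96·exp(−0.0578 × 11.89) + 0.04·exp(−0.0578 × 6 − 1.5 × 0.0578 × 5.89) = 0.483 + 0.017 = 0.500.

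Larger shares show how the effect grows. At c = 20% (5 of 25) the differences are 3.5 and 9.4 weeks; at c = 40% (10 of 25) they are 3.0 and 7.3 weeks. Nothing in the protocol suggests shares of that size.

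**6. Limits of the effect.** If treatment comes at or after the control median, S(*m*) is already 0.5 before anyone switches, so the median difference does not change for any *c*. Treatment after healing cannot alter that patient's healing time at all. Quality of life and costs are collected to 12 months regardless of healing, so they remain exposed to later treatment; if crossover gave the full benefit (a further assumption), the 12-month quality-of-life contrast would shrink by the share *c* itself.

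**The case against.** A reader might infer that the gap exists because controls have no index procedure. The documents do not support that: the criteria are met before allocation, and exclusion 3 already treats every candidate as someone who might be treated. That leaves only an unclear anchor, and it stands as a wording point.

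A reader might also infer that the control arm will be substantially contaminated, for instance from the opening statement of the protocol, "Minimally invasive techniques are now routine for the treatment of lower limb varicose veins". That sentence is about varicose veins; it is no evidence that ulcer patients at this clinic are already on a list for ablation, and the protocol defines their normal treatment as dressing and compression. No booking rate is given. The uncovered 92% of follow-up overstates the exposure of the healing endpoint for the reason in step 6.

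The strongest objection is that the protocol openly allows later vascular intervention in either arm, without a time limit. A control not booked at entry could be listed soon afterwards and treated in the same week. Changing exclusion 8 therefore removes only part of the contamination, and the documents do not show how large a part. This stands. So does the fact that such interventions are already recorded, and that the comparisons are described as exploratory in a pilot. How crossovers enter the analysis may be covered in a statistical analysis plan that is not shown.

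What these points do not remove is the difference in kind. Intervention that becomes necessary during follow-up is a care decision. A date fixed before entry is known at screening, and an analysis plan cannot take such a patient out again after randomisation without damaging the randomised comparison. The exploratory label does not help either, since the descriptive control results are themselves what the pilot delivers.

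**Conclusion.** The point holds in a limited form. Exclusion 8 is the only rule on booked procedures, and it is too short for a 12-month comparison with a control arm that should have no vein treatment. Any control already booked for treatment of the study vein after the window biases the contrast toward no difference. The anchor is a separate ambiguity.

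The size is unknown. One such control is 4% of the arm and, under the assumed exponential model with treatment at week 6, costs about 3% to 5% of the difference in median healing time; with bookings at or after the control median it costs nothing on that measure. The 12-month quality-of-life and cost comparisons stay open to it. The documents do not support a claim of large dilution, nor a claim that any booked patient will in fact enter. The change is worth making because it is cheap and the problem is avoidable at screening.

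**What to change.** Reword exclusion 8 so that it is judged at randomisation for all candidates and excludes any venous intervention on the study limb already planned within the 12-month follow-up. Keep the 30-day rule, also counted from randomisation, for other planned procedures.

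Leave the offer of later intervention under Procedure / Intervention Description as it is. The protocol already records such interventions, so add only the date and whether the study vein was treated, and report the count by arm.

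The cost is one reworded criterion and a small addition to the case report form. A few already-listed patients become ineligible, which may slow recruitment of the 50 slightly. The change limits contamination booked before entry; it does not touch intervention that arises during follow-up.

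### Adverse events, a primary objective, are scheduled only at baseline, 3, 6 and 12 months and are not tied to the weekly visits, so short-lived events after the procedure may be under-counted

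*Protocol*

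**What the plan says.** Under Primary Objectives, item 4 asks: "What is the adverse effect profile of VenaSeal[™] cyanoacrylate occlusion of incompetent lower limb veins for the treatment of venous leg ulcers". Under Secondary Endpoints, the list opens with "The secondary measures will be measured at baseline, 3, 6 and 12 months and are as follows", and item 4 of that list reads "Adverse event recording will also take place, which is an important step in defining the safety of the procedure for this purpose". The protocol gives no other timing, definition or method of asking for adverse events.

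Two kinds of contact are described. Study Design states: "Patients will be followed up via face-to-face consultations at 3, 6 and 12 months post-randomisation". Primary Endpoints adds ulcer tracings every 7 days, give or take 2, taken in duplicate by two research team members, and the procedure section has treated patients back at the leg ulcer clinic weekly for wound care and bandaging. The weekly contact is open-ended only until the ulcer closes: "Once healing has occurred, the patient will not be required to return to the clinic for weekly assessments".

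The Statistical Method section presents the number and percentage of adverse events in each group and names chi-squared tests among the between-group comparisons. It mentions no allowance for length of observation.

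**The concern.** The only schedule attached to adverse events is the quarterly-to-half-yearly one used for questionnaires and duplex scans. Phlebitis or an access-site infection would be expected soon after the procedure and may well have resolved by 3 months. A first record at 3 months then depends on what the patient remembers or what happens to be in the notes.

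The weekly visits could close this gap, but their stated purposes are ulcer measurement and ulcer care. By contrast, the protocol says outright that the research team will record further venous interventions at any time within 12 months. It makes no such statement for adverse events.

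If staff do note events at the weekly visits, a different difficulty follows. Those visits stop at healing, and healing time is what the treatment is meant to shorten. A plain count per group then mixes event frequency with length of close observation.

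At stake is one of four primary objectives, in a population where the protocol says this treatment has not been studied, and in a pilot meant to inform a larger trial. An analysis plan cannot recover events that were never recorded, so this belongs in the protocol.

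**Working it through.** The protocol gives no figure to reproduce here. The check is first textual, then an illustration of size.

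**The text under its two readings**

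- Reading A, the schedule as written: events are recorded at baseline, 3, 6 and 12 months. Both arms share the schedule, and healing does not alter it. The weakness is late recording of early events.
- Reading B, ongoing recording at weekly visits: early events are mostly seen promptly. The weakness is that close observation ends at healing.

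The two weaknesses belong to different readings and should not be added together.

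**Size under reading A**

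Inputs from the protocol: 25 patients per arm (Study Design); "mild phlebitis reported in 6-16% of patients" (Background). Assumptions: that rate carries over to ulcer patients, and recording at 3 months captures 50-90% of cases.

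- Expected true cases: 25 × 0.06 = 1.5 and 25 × 0.16 = 4.
- Expected recorded cases: 1.5 × 0.5 = 0.75 at the lowest, 4 × 0.9 = 3.6 at the highest.
- Chance of recording no case = (1 − rate × capture)^25:

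| True rate | Full capture | 90% capture | 50% capture |
|---|---|---|---|
| 6% | 0.94^25 = 21% | 0.946^25 = 25% | 0.97^25 = 47% |
| 16% | 0.84^25 = 1.3% | 0.856^25 = 2.1% | 0.92^25 = 12.4% |

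At 90% capture the loss is negligible. At 50% and a true rate of 6%, the chance of reporting no phlebitis at all is close to one half.

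**Size under reading B**

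The protocol gives no healing times, so exponential healing is assumed, with L = ln 2 / median.

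- Share still unhealed, and so still seen weekly, at t weeks = exp(−L·t). For medians of 6, 12 and 24 weeks this is 79%, 89% and 94% at week 2, and 63%, 79% and 89% at week 4. Most patients are still under weekly observation early on.
- Mean weekly contact within T weeks = (1 − exp(−L·T))/L. Take medians of 16 weeks (control) and 10 weeks (VenaSeal), with full capture while attending weekly and 50% afterwards. Over the first 4 weeks, contact is 3.67 against 3.49 weeks.
- Capture = (contact + 0.5 × (4 − contact))/4 = 0.959 against 0.937. Ratio VenaSeal to control: 0.937/0.959 = 0.98. With 4 cases expected, the difference is 4 × (0.959 − 0.937) ≈ 0.1 case.
- Over 52 weeks, contact is 20.7 against 14.0 weeks, capture is 0.699 against 0.635, and the ratio is 0.91. This holds only if events arise at a constant rate throughout the year, so it describes later events and not those soon after the procedure.

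**The case against.** The best defence is that the list heading is loose. The same heading covers visit frequency and costs, which accumulate over time and cannot be measured at a point. Item 4 has its own sentence, saying that recording will also take place, which could mean ongoing recording. A review at a visit normally covers the interval since the last one. Complications of treatment are also to be costed. With research staff measuring unhealed ulcers weekly, a phlebitis or wound infection is unlikely to surface first at 3 months. The trial is a small pilot whose comparisons are declared exploratory.

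Much of this stands. A reader might infer that early events definitely rest on patient recall. The documents do not support that as fact: it follows from the schedule as written, but most patients would still be attending weekly in the first weeks. A reader might also infer that detection is biased in favour of VenaSeal. The stopping rule is the same in both arms, so contact differs only if healing times differ, and the effect on early events is small. Events at the access site or from the adhesive have no counterpart in the control arm in any case.

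What the defence does not supply is any sentence saying that adverse events are asked about or recorded at weekly visits. Pilot status does not excuse this either, since descriptive safety data are a main product of the pilot.

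**Conclusion.** The point holds as a defect in the stated collection schedule. Adverse event recording serves a primary objective, but the only timing given for it is baseline, 3, 6 and 12 months.

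Read as written, short-lived events may be under-counted. How seriously depends on capture, from almost nothing at 90% to a substantial loss at 50%. This rests on the 6-16% rate from studies outside the ulcer population and on an assumed capture range.

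Read as ongoing recording, crude numbers and percentages per group may not be comparable if healing times differ, mainly for events after healing. The healing medians and the 50% capture after healing are assumptions.

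The change should be made. It does not threaten the healing outcomes or the trial's overall validity.

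**What to change.** Take adverse events out of the list measured at baseline, 3, 6 and 12 months and give them their own paragraph:

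- Record events with onset dates, from randomisation, using the same short checklist in both arms, at every weekly visit and again at 3, 6 and 12 months.
- Report patients with at least one event, out of all randomised in the arm, over a common early window that does not depend on healing. The protocol fixes no interval from randomisation to procedure, so the window must be long enough to include the procedure and the weeks after it.
- Contact patients who have already healed briefly at the end of that window, with the same checklist.
- Show later events separately, alongside the length of weekly observation in each arm.

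The cost is one protocol paragraph, a one-page form, a few minutes at visits that already take place, and a few brief contacts. The recorded event count will probably be higher, which should be expected when the results are set beside earlier studies.
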